#### 5.4.1 Descriptive Statistics

Descriptive statistics will be calculated for both study cohorts. Categorical variables will be summarized by frequencies and proportions, and continuous variables will be summarized by means and standard deviations or medians and interquartile ranges. Differences between study cohorts will be assessed using Chi-square tests for categorical data and t-tests or Wilcoxon rank-sum tests for continuous data, as indicated.

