Another study published by in January of 2018 described a linkage study between the National Joint Registry, Hospital Episodes Statistics and records of the Office for National Statistics on deaths. Patients who underwent elective total hip arthroplasty between January 2003 and December 2014 with no past history of cardiac failure were included and stratified as having either a MoM (n = 53 529) or a non-MoM (n = 482 247) arthroplasty. The primary outcome measure was the time to an admission to hospital for cardiac failure or death. Analysis was carried out using data from all patients and from those matched by propensity score. The risk of cardiac failure was lower in the MoM cohort compared with the non-MoM cohort (adjusted hazard ratio (aHR) 0.901; 95% confidence interval (CI) 0.853 to 0.953). The risk of cardiac failure was similar following matching (aHR 0.909; 95% CI 0.838 to 0.987) and the findings were consistent in subgroup analysis.

Goodnough et.al. published a study designed to compare the rate of onset of new cardiac symptoms in patients who have undergone MoM THA with those who have undergone metal-on-polyethylene (MoP) THA. Data from the Medicare Standard Analytics Files database for patients who underwent MoM THA between 2005 and 2012 was used. Bearing surface was selected using International Classification of Diseases ninth revision codes. Patients with a minimum five-year follow-up were selected. An age and gender-matched cohort of patients, who underwent MoP THA served as a comparison group. New diagnoses of cardiac disease including congestive heart failure were collected during the follow-up period. We identified 29 483 patients who underwent MoM THA and 24 175 matched patients who underwent MoP THA. Both groups had a mean Charlson comorbidity index score of 4. There were no statistically significant differences in 30 of 31 pre-existing comorbidities. Patients undergoing MoM THA had a slightly lower incidence of cardiac failure compared with those undergoing MoP THA at three years (6.60% versus 7.06%, odds ratio (OR) 0.93, 95% confidence interval (CI) 0.87 to 0.99) and four years (8.73% versus 9.49%, OR 0.91, 95% CI 0.86 to 0.97) postoperatively, with no difference in the incidence of new cardiac failure in between the groups at five years. There was no statistically significant difference in the incidence of arrhythmia, myocardial infarction and cardiomyopathy at any time between the two groups.

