#### 4.2.2 Secondary objective(s):

• To describe and compare the baseline characteristics of the exposure groups and to identify important prognostic variables that should be balanced between the exposure groups and which should be included in the propensity score of the primary analysis.

[figure not shown]

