#### 5.3.3.3 Outcomes for Secondary Objective(s)

• Variables noted in sections above

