#### 5.3.4 Sample Size and Study Power

A previous analysis of the Medicare SAF database identified 18,521 patients with MoM hip implants between 2005 and 2015.

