#### 5.4.3 Risk of Heart Failure Associated with MoM Implants

Cox proportional hazards regression will be performed to determine HRs of heart failure with 95% Cis in MoM implants versus non-MOM implant and MoM implants versus RA patients without arthroplasty. Propensity score matching or stratification will be used to control for confounding.

If a significantly higher risk of heart failure is identified for patients with MoM implants, Cox proportional hazards regression will be conducted to determine risk factors for a diagnosis of heart failure.

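### The baseline comparison meant to guide the propensity score rests only on between-group significance tests, which show association with exposure and not with heart failure

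*Protocol*

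**What the plan says.** Protocol 4.2.2 sets one secondary objective. It asks for the groups' baseline profiles to be set side by side and, from that, "to identify important prognostic variables that should be balanced between the exposure groups and which should be included in the propensity score". Section 5.3.3.3 gives the data for this objective only as "Variables noted in sections above", meaning the demographic, procedural, clinical and provider variables listed under 5.3.2.

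Section 5.4.1 gives the method for comparing groups: "Differences between study cohorts will be assessed using Chi-square tests for categorical data and t-tests or Wilcoxon rank-sum tests for continuous data". It names no measure of the size of an imbalance and no limit for acceptable balance.

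Section 5.4.3 then states: "Propensity score matching or stratification will be used to control for confounding". The same section contains the only model that relates covariates to heart failure. That model is run after the primary result, and only if MoM patients prove to be at significantly higher risk.

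The only study size given is in 5.3.4: "A previous analysis of the Medicare SAF database identified 18,521 patients with MoM hip implants between 2005 and 2015". The protocol does not give the sizes of the non-MoM and osteoarthritis comparators.

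**The concern.** Two different questions are put to one tool. A propensity score needs the variables that predict heart failure, above all those that also differ between groups. A chi-square, t or Wilcoxon test between exposure groups answers only whether a variable differs by exposure, and its p-value mixes the size of that difference with the number of patients. It cannot show that a variable is prognostic.

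If the tests were used as the guide, variables that mainly predict implant choice would look important. Section 5.3.2.4, for example, lists hospital and surgeon volume for the specific arthroplasty type. A strong predictor of heart failure that happened to differ little would look unimportant. This matters because the propensity score is the only control for confounding that the protocol states, for both co-primary comparisons in a non-randomised study.

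**Working it through.** **Which tools are available before the primary analysis.** Section 4.2.2 asks for prognostic variables. Section 5.4.1 supplies tests against exposure. The covariate-outcome model in 5.4.3 comes after the primary result and is conditional on it, so it cannot inform the score. No tool named before the primary analysis relates a covariate to heart failure.

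**How sensitive the tests are.** The protocol has no figure of its own to reproduce: 5.3.4 gives a count from an earlier analysis, with no power or alpha.

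Inputs:
- MoM group n1 = 18,521 (5.3.4).
- Comparator n2 = k × n1, with k from 0.5 to 10 (assumed, because no size is given).
- Two-sided 5% level (assumed).

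Smallest standardised mean difference (SMD) that reaches p<0.05 = 1.96 × √(1/n1 + 1/n2):

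| k | Calculation | SMD |
|---|---|---|
| 0.5 | 1.96 × √(3/18,521) | 0.025 |
| 1 | 1.96 × √(2/18,521) | 0.020 |
| 2 | 1.96 × √(1.5/18,521) | 0.018 |
| 5 | 1.96 × √(1.2/18,521) | 0.016 |
| 10 | 1.96 × √(1.1/18,521) | 0.015 |

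In natural units at 1:1:
- A comorbidity with 20% prevalence is significant at 1.96 × √(2 × 0.20 × 0.80/18,521) = 0.0081, or 0.8 percentage points.
- Mean age, with an assumed SD of 6 years, is significant at 0.0204 × 6 = 0.12 years.

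Power to flag a small imbalance:
- SMD 0.03: 65% (k = 0.5), 82% (k = 1), 97% (k = 10).
- SMD 0.05: about 98% at k = 0.5 and higher at every larger ratio.

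Against the conventional guide of 0.10, which is not in the protocol, none of these differences would count as a notable imbalance.

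**Scale check from the protocol's background.** Section 3 cites a study in the same database with "29 483 patients who underwent MoM THA and 24 175 matched patients who underwent MoP THA", and three-year cardiac failure of 6.60% versus 7.06%. This is an outcome difference and is used here only to show scale.
- Odds ratio = (0.0660/0.9340)/(0.0706/0.9294) = 0.93, 95% CI 0.87 to 0.995. This matches the cited 0.93 (0.87 to 0.99) to rounding.
- Pooled proportion = (29,483 × 0.0660 + 24,175 × 0.0706)/53,658 = 0.0681. Then z = −0.0046/√(0.0681 × 0.9319 × (1/29,483 + 1/24,175)) = −2.10, p = 0.035.
- SMD = −0.0046/√((0.0660 × 0.9340 + 0.0706 × 0.9294)/2) = −0.018.

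A difference of 0.018 standard deviations was therefore significant at a size comparable with this study's.

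**The case against.** The strongest reply is that 5.4.1 is a descriptive section. It states no alpha and no selection threshold and does not mention the propensity score. Section 4.2.2 does not say that prognostic variables are identified by significance test, and detailed covariate selection may sit in a statistical analysis plan that is not shown. Much of this stands. A reader might infer that the protocol selects covariates by p-value; it does not say so, and the link comes from reading the two sections together. What remains is that the protocol makes the comparison serve the propensity score and names only this tool for it.

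Several stronger readings are tempting but unsupported:

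- *Balance after matching would be judged by p-values.* The protocol does not plan to repeat the tests after matching.
- *Small strata would hide large imbalances.* No within-stratum baseline tests are planned. With five equal propensity strata at 1:1 (assumed), there would be 18,521/5 ≈ 3,704 per group, and the smallest significant SMD would be 1.96 × √(2/3,704) = 0.046, still below 0.10. An SMD of 0.10 becomes non-significant only below about 770 per group.
- *Nearly every variable would be flagged.* The cited study in the same database found 30 of 31 pre-existing comorbidities not significantly different. That cohort was matched on age and gender, so it is not a direct guide to the unmatched comparison here, but it shows that flagging is not automatic.
- *Standardised differences would identify the prognostic variables.* They would not, because they also measure association with exposure only. They improve the measurement of balance; choosing covariates needs a separate step.

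It is also fair to say that subject-matter thinking is already present. Section 5.3.2.3 lists cardiovascular comorbidities and conditions linked to mortality, so the candidate list does not come from the tests.

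**Conclusion.** The point holds as an improvement to the method. As written, the protocol asks the group comparison to reveal prognostic variables and equips it only with tests of association with exposure. At about 18,521 MoM patients, those tests become significant at standardised differences of 0.015 to 0.025, over assumed comparator ratios of 10 to 0.5 and at an assumed two-sided 5% level. The mismatch between tool and purpose does not depend on those assumptions.

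A reader might go further and conclude that the hazard ratio will be biased or its variance inflated. The documents do not support that: no selection rule is fixed, and no effect on the hazard ratio can be calculated from what is given. The endpoint and the Cox model are not touched. This is a nearly free improvement and does not invalidate the primary analysis.

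**What to change.** In 4.2.2, state that propensity score covariates are chosen from the listed baseline variables by prior knowledge of heart failure risk, whatever differences are observed between groups, and that the choice is fixed before outcomes are analysed. Section 5.3.2.3 also lists two post-index items (dislocation or instability, and metallosis). These are not baseline variables and should not be candidates.

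In 5.4.1, state that balance is assessed by standardised mean differences, reported before and after matching or stratification, with 0.10 as a conventional guide. P-values may still be shown, but not as the measure of balance.

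The cost is a few sentences in two sections and extra columns in the baseline table. No further data are needed, and nothing now reported is lost.

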#### 5.4.2 Incidence Rate of Heart Failure

The number of new cases of heart failure will be determined. Person-time for each patient will be calculated from 30 days after index date to the first diagnosis code of heart failure (at-risk time interval). The incidence rate of heart failure will be determined for each study cohort as the number of new cases of heart failure during the observation period divided by the total person-time of observation among the patients at risk. The results will be reported as a point estimate (in cases/1000 person-years) and

95% CI. Confidence intervals will be based on asymptotic theory assuming the outcome follows a Poisson distribution.

#### 5.4.3 Risk of Heart Failure Associated with MoM Implants

Cox proportional hazards regression will be performed to determine HRs of heart failure with 95% Cis in MoM implants versus non-MOM implant and MoM implants versus RA patients without arthroplasty. Propensity score matching or stratification will be used to control for confounding.

If a significantly higher risk of heart failure is identified for patients with MoM implants, Cox proportional hazards regression will be conducted to determine risk factors for a diagnosis of heart failure.

#### 5.4.4 Sensitivity Analyses

- Limit outcome to hospitalization for heart failure
- Stratification by ICD-9 and ICD-10 codes (ICD-10 codes may be improved for ascertaining both MoM prostheses use and for heart failure as compare to ICD-9 codes)
- Stratification for non-MoM comparison (exclude MoP from the comparator group)

## 5.5 Quality Control

The study will be completed per the quality control guidance adopted by the individual/ champion evidence generation functions.

## 5.6 Limitations of the Research Methods

As with any database study, identification of medical events, such as heart failure or co-morbidities, is limited to data that are captured as part of the medical record or claims, which are not primarily collected for research purposes, and will rely on appropriate diagnostic codes to detect these events. Misclassification bias can result if study patients are not categorized correctly with regards to exposure or outcome. Limited patient follow-up time will hinder our ability to study the long-term risk of heart failure. The study results will be generalizable to patients meeting the inclusion and exclusion criteria.

## 6. Protecting the Confidentiality of the Data Obtained

Confidentiality of patient records will be maintained at all times. All study reports will contain aggregate data only and will not identify individual patients or physicians. At no time during the study will the Johnson & Johnson MD company receive patient identifying information except when required by law.

## 7. Management and Reporting of Complaints and Adverse Events

In this study, potential product complaints or safety signals cannot or will not be identified. Thus, the minimum criteria for reporting a product complaint or adverse event (i.e., suspect device manufacturer and event) will not be met.

## 8. Plans for Disseminating and Communicating Study Results

A final report will be created from study results which may be considered for publication in a peer reviewed publication according to the J&J Publication Policy.

# 10. Appendices

- 1. Appendix I [Text goes here]
- 2. Appendix II [Text goes here]
- 3. Appendix III [Text goes here]
- 4. etc.

# 11. Major Amendments

#	Date	Section of study protocol	Amendment or update	Reason
1				
2				
3				

# **12.** Project Milestones

This is illustrative. Please revise based on study timelines.

Task Name	Time to Completion (in weeks)
Develop JJ-format protocol	3 weeks from finalization of research proposal
Receive feedback from Stakeholder	1 week after provision of draft protocol
Finalize Protocol	1 week after receiving feedback from Stakeholder
Finalize Data Specification and Attrition File	1 week after finalization of protocol
Provide Patient Attrition Flow and Counts	1 week after finalization of data specification file
Build analytic file	6 weeks after attrition flow
Conduct analyses	Descriptive analyses: 2 weeks after completion of analytical file Multivariate analyses: 4 weeks after completion of analytical file
Prepare final report	Final report: 3 weeks after completion of analyses
Total Timeline till Final Report	20 weeks from finalization of research proposal
Additional Tasks	
Prepare abstract for conference submission	TBD based on timing of selected conference
Develop conference presentation or poster	TBD based on timing of selected conference
Prepare Journal Manuscript	TBD
